12.3 Additional Efficacy Analyses

- Time to detection of MABC (in days) in liquid growth medium at baseline and the Day 28, 56, 84 and Day 84/EOT visits will be summarized by treatment group, including n, mean, SDs, median, minimum and maximum.
- The number and percentage of subjects who convert from a positive MABC sputum culture at baseline to a sputum culture negative for MABC at any time post-baseline and at the Day 28, 56, 84 and Day 84/EOT visits and who do not convert to a negative culture (i.e., remain positive) will be summarized by treatment group.
- In those subjects whose first negative culture (i.e., convert from a positive MABC culture at baseline to a negative MABC culture) is on the Day 28, 56, 84 and Day 84/EOT visits, the number and percentage of subjects with a culture positive for *M. avium* or other non-abscessus mycobacterium species at baseline and at the visit will be summarized by treatment group.
- The number and percentage of subjects who convert from a positive MABC culture at baseline to a sputum culture negative for MABC by the Day 56 visit and have no subsequent positive MABC culture will be presented, as well as the number and percentage of subjects who convert to a negative culture by the Day 56 visit and have a subsequent positive culture, and those who do not convert to a negative culture by Day 56 will be summarized by treatment group.
- The number and percentage of subjects who convert from a positive MABC sputum culture at baseline to a sputum culture negative for MABC or growth of MABC only in liquid medium at any time post-baseline and at the Day 28, 56, 84 and Day 84/EOT visits and who do not convert to a negative culture will be summarized by treatment group.
- The number and percentage of subjects whose first negative culture (i.e., convert from a positive MABC culture at baseline to a negative MABC culture) is on the Day 28, 56, 84 and Day 84/EOT visits will be summarized by treatment group.
- A shift table of the semi-quantitative score from baseline to Days 28, 56, 84 and EOT visits will be presented by treatment group.
- Quantitative mycobacterial load (CFU/mL) and semi-quantitative score of the MABC at baseline and the Day 28, 56, 84 and Day 84/EOT visits will be summarized by treatment group, including including n, mean, SDs, median, minimum, and maximum, geometric mean, 95% CI of geometric mean, and %CV for mycobacterial load and number and percentage of subject of each semi-quantitative score.
- For each definition of the primary endpoint, the number and percentage of subjects with a clinical response and who had culture conversion (ie, converted from a positive MABC sputum culture at baseline to a negative sputum culture at the Day 84 visit), clinical response and did not have culture conversion, clinical nonresponse and had culture

conversion, and clinical nonresponse and did not have culture conversion, will be presented by treatment group.

- The cumulative distribution of the change from baseline to the Day 84 visit in the respiratory domain of the QOL-B by PGI-S (categorized as improved vs. no change/worsened) will be provided as a graph.
- Descriptive statistics of the change from baseline to the Day 84 visit in the respiratory domain of the QOL-B in subjects who converted from positive MABC sputum culture at baseline to a negative sputum culture at the Day 84 visit, by treatment group will be presented.
- A subject will be defined as a responder if all 3 of his/her most bothersome symptoms at baseline are absent or mild at the Day 84 visit and a non-responder if at least one of the most bothersome symptoms is worse than mild. The number and percentage of subjects defined as a responder and nonresponder will be presented by treatment group.
- A sample is considered positive if there was any growth in broth or agar. A sample is considered negative if there was no growth in broth and agar.

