6.2 Inclusion Criteria

Subjects must meet all of the following criteria at Screening and/or Baseline to be eligible to participate in the study:

1. Written and signed informed consent must be obtained before any protocol-specific assessment is performed.
2. Male and female subjects age 18 years or older.
3. Diagnosed MABC pulmonary disease as per Infectious Diseases Society of America/American Thoracic Society guidelines criteria. Subjects must have:
 - At least 2 of the following NTM-infection symptoms at Screening and Baseline:
 - Chronic cough, coughing up blood (hemoptysis), wheezing, chest pain, frequent throat clearing, phlegm or sputum production, shortness of breath, fatigue, fever, night sweats, poor appetite, and/or weight loss
 - At least 1 positive pulmonary culture for MABC in the 6 months prior to Screening and 1 positive culture at Screening (note: prior culture and screening cultures must be at least 30 days apart).
 - Radiographic evidence of MABC infection via computed tomography (CT) scan of the chest within 3 months prior to Screening with findings consistent with NTM pulmonary disease. If no CT scan obtained within previous 3 months, one should be performed at Screening to confirm eligibility.
4. Based on the clinical assessment of the investigator, guideline-directed antibiotic therapy for treatment of MABC will not be required within the next 3 months, and a delay, in order for the subject to participate in a placebo-controlled clinical trial, is considered reasonable and clinically acceptable.
5. Be able to produce approximately 5 mL of sputum via spontaneous expectoration or be willing to undergo sputum induction to produce approximately 5 mL of sputum for microbiological evaluation.
6. Females must have a negative serum pregnancy test and agree to use a highly effective form of birth control (eg, abstinence, oral contraceptive, intrauterine device, or barrier contraception [eg, condom], tubal ligation, hysterectomy, bilateral oophorectomy, postmenopausal or vasectomized partner) from Screening through study completion. Males (if sexually active) must agree to use a highly effective method of birth control with female partner(s) from Screening through study completion.

7. Able and willing to adhere with the requirements and restrictions of the study.

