10.2.2 Baseline Analyses

The following will be provided for the baseline MABC specimen:

- Baseline positive culture for MABC and by subspecies, as well as MAC and other mycobacterium.
- Distribution of the semi-quantitative score defined as follows:

Semi-quantitative culture scores	Growth in broth	Growth on agar plate	CFU/mL on an agar plate
0	-	-	0
1	+	-	0
2	+/-	+	1 - <50
3	+/-	+	50-99
4	+/-	+	100-199
5	+/-	+	200-299
6	+/-	+	≥300

- Distribution of MIC to amikacin, cefoxitin, ciprofloxacin, clarithromycin, clarithromycin-D14, clofazimine, doxycycline, imipenem, linezolid, minocycline, moxifloxacin, omadacycline, tigecycline, and trimethoprim/sulfamethoxazole
- Susceptibility profile (interpreted as resistant, susceptible and intermediate according to CLSI breakpoints) to each antibiotic with defined breakpoints
- Multidrug Resistance (MDR) defined as nonsusceptibility (MIC value interpreted as “I” or “R”) to at least one agent in three or more antimicrobial categories. Agents that do not have susceptibility interpretations i.e. those in Table 10.3.2 with ‘N/A’ will not be considered in this analysis.
- MIC range, MIC₅₀ and MIC₉₀ to omadacycline

Table 10.3.2. Antimicrobial Categories, Agents and CLSI Breakpoints

Antimicrobial Category for MDR evaluation	Antimicrobial Agent	MIC ug/mL		
		S	I	R
Aminoglycoside	Amikacin	≤16	32	≥64
Cephalosporin	Cefoxitin	≤16	32-64	≥128
Fluoroquinolone	Ciprofloxacin	≤1	2	≥4
Macrolide	Clarithromycin	≤2	4	≥8
N/A	Clofazimine	N/A	N/A	N/A
Tetracycline	Doxycycline	≤1	2-4	≥8
Carbapenem	Imipenem	≤4	8-16	≥32
Oxazolidinone	Linezolid	≤8	16	≥32

N/A	Minocycline	N/A	N/A	N/A
Fluoroquinolone	Moxifloxacin	≤1	2	≥4
Antifolate	Trimethoprim-sulfamethoxazole	≤2/38		≥4/76
N/A	Tigecycline	N/A	N/A	N/A

S=Susceptible, I=Intermediate, R=Resistant

Clinical and Laboratory Standards Institute. Performance Standards for Susceptibility Testing of Mycobacteria, Nocardia spp., and Other Aerobic Actinomycetes 1st ed. CLSI document M62. 2018. CLSI, [name].

Microbiology results will be incorporated into several of the efficacy analyses, as defined in Section 11.1.

The by-subject listings noted below will also be provided. On each listing, all samples will be presented and the baseline and post-baseline samples selected as indicated above will be indicated with a flag.

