84/EOT visits, the number and percentage of subjects with a culture positive for *M. avium* or other non-abscessus mycobacterium species at baseline

- The percentage of subjects who convert from a positive MABC culture at baseline to a sputum culture negative for MABC post-baseline (through the Day 56 visit) and have no subsequent positive MABC sputum culture during the study
- The number and percentage of subjects who convert from a positive MABC sputum culture at baseline to a sputum culture negative for MABC or with MABC growth only in liquid medium at any time post-baseline and at the Day 28, 56, 84 and Day 84/EOT visits
- Quantitative mycobacterial load (CFU/mL) and semi-quantitative score of the MABC at baseline and the Day 28, 56, 84 and Day 84/EOT visits

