12.2.10 Time to Growth in Liquid Medium Only

Kaplan-Meier methods will be utilized to determine the time to growth in liquid medium only for MABC for the ITT Analysis Set by treatment group. The analysis will be limited to subjects with growth on agar plate at baseline in the ITT Analysis Set. Time to growth in liquid medium only will be defined as the number of days from the date of test article administration to the date of the first assessment where growth is detected in liquid medium only. If there is no sputum sample indicating growth in liquid medium only but there is a negative culture (defined in Section 12.2.11), the date of the first negative culture will be used for the determination of time to growth in liquid medium only.

Subjects who died, withdrew from the study, or received alternative antibiotic therapy (not including chronic macrolides) for treatment of the NTM infection prior to growth in liquid medium only for MABC (or a negative culture, if no sputum sample indicating growth in liquid medium only) will be censored at the date of the death, study withdrawal, or the start date of the alternative antibiotic therapy respectively. Subjects who have a positive sputum culture (defined as growth in both liquid medium and agar plate [growth on both LJ slant and biplate]) through Day 84 will be censored at the date of the Day 84 visit.

The median, 25th and 75th percentile for time to growth in liquid medium only will be provided with 2-sided 95% CIs for each treatment group. A p-value will be determined using a stratified (by prior antibiotic use) log-rank test. Kaplan-Meier curve for time to growth in liquid medium only will be provided in a figure.

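### The negative-or-liquid-only conversion count does not require agar growth at baseline, so a subject who stays liquid-only throughout is counted as a converter

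*SAP*

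**What the plan says.** SAP 11.1 lists, among the additional efficacy endpoints, the number and percentage of subjects who start MABC-positive and later have "a sputum culture negative for MABC or with MABC growth only in liquid medium at any time post-baseline"; by-visit counts follow the same definition. The matching bullet in SAP 12.3 describes the move as "to a sputum culture negative for MABC or growth of MABC only in liquid medium at any time post-baseline". It then names the other group as those who do not reach a negative culture.

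The last bullet of 12.3 defines the start state: "A sample is considered positive if there was any growth in broth or agar". A sample is negative only if neither medium grows.

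SAP 12.2.10, the time-to-event analysis of growth in liquid medium only, carries a restriction that the conversion bullet lacks: "The analysis will be limited to subjects with growth on agar plate at baseline in the ITT Analysis Set". Its censoring rule also uses a narrower meaning of positive: "Subjects who have a positive sputum culture (defined as growth in both liquid medium and agar plate".

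**The concern.** A conversion endpoint needs start and end states that do not overlap. In the plain positive-to-negative bullets they do not. In this one they do, because liquid-only growth counts both as positive at baseline and as converted afterwards. A subject can be scored as a microbiological success with no change in culture, in either arm.

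The complement has a second overlap. A subject whose post-baseline culture grows only in liquid is a converter under the first half of the bullet and a non-converter under the second half. This applies even to subjects who started with agar growth, so the two reported groups need not add up to the number analysed.

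At stake is the accuracy of one descriptive percentage per arm and visit, and its comparability with the 12.2.10 analysis.

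**Working it through.** **Plan's own figure.** The documents give no expected rate, power or precision for this endpoint, so there is no stated figure to reproduce. The check is of definitions, followed by simple counts.

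**Step 1. Can a subject be liquid-only at baseline?** Yes.
- The semi-quantitative table in SAP 10.2.2, which describes the baseline MABC specimen, includes score 1: broth positive, agar negative, 0 CFU/mL.
- Protocol 6.2 asks for "At least 1 positive pulmonary culture for MABC in the 6 months prior to Screening and 1 positive culture at Screening", with no condition on solid medium.
- SAP 10.2.1 takes as baseline the MABC-positive sample nearest to, but before, first dose, again with no agar condition. A subject with agar growth at Screening can therefore have a liquid-only baseline if a later pre-dose sample grows only in broth.

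**Step 2. Trace an unchanged subject through the definitions.**

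| Time | Result | Rule applied | Status |
|---|---|---|---|
| Baseline | score 1 (broth +, agar −) | 12.3: any growth is positive | meets start state |
| Day 28 | score 1 (broth +, agar −) | 11.1 and 12.3: liquid-only growth qualifies | counted as converted |

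Nothing in 11.1 or 12.3 removes this subject.

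**Step 3. Trace the same Day 28 result through the complement.** The culture is not negative, because broth grows. The subject therefore also belongs among those who have not reached a negative culture. One result falls in both categories.

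**Step 4. Which other endpoints share the problem?**
- 12.2.9 needs a reduction in score, so 1 to 1 is not a success.
- 12.2.10 admits only subjects with agar growth at baseline.
- 12.2.11 needs no growth in either medium.
- The primary endpoints use symptoms only.

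No primary or secondary endpoint is affected.

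**Step 5. Size.** Let f be the share of subjects who are liquid-only at baseline. The documents do not give it, so the values below are assumptions. Take f equal in both arms, all 45 and 30 planned subjects evaluable, and all liquid-only subjects staying liquid-only. Unchanged subjects counted as converters = f × n:

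| f | Omadacycline (n = 45) | Placebo (n = 30) |
|---|---|---|
| 0% | 0 | 0 |
| 5% | 2.25 | 1.5 |
| 10% | 4.5 | 3 |
| 20% | 9 | 6 |

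These are upper figures for each f. If only 70% of the liquid-only subjects stayed liquid-only, f = 20% would give 0.7 × 9 = 6.3 and 0.7 × 6 = 4.2.

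If p is the conversion rate among subjects with agar growth at baseline, and all liquid-only subjects stay so, the reported rate is f + (1 − f)p. The excess over p is f(1 − p), which is never more than f.

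**The case against.** Several points on the other side are sound.

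- **Low tier.** The endpoint is an additional one, summarised only as number and percentage by arm. No test, interval or odds ratio is planned for it, and the SAP calls the study exploratory for efficacy.
- **Visible elsewhere.** Section 12.3 also plans a shift table of the semi-quantitative score and the distribution of scores at each visit. A reader can find the subjects who stay at score 1, and their number at baseline by arm. This limits the harm but does not correct the reported percentage.
- **The word convert implies change.** It does, but no rule excludes an unchanged liquid-only subject, and programming follows the stated definitions.
- **Positive means growth in both media in 12.2.10.** That wording belongs to the censoring rule there and conflicts with the any-growth rule in 12.3, the section that governs this bullet. If it did apply, liquid-only growth would be neither positive nor negative, so the text would still need repair.

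Stronger readings are tempting and are not supported.

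- **No baseline condition at all.** A positive MABC culture is required. Only an agar condition is missing.
- **A diluted treatment effect.** Suppose the 45% and 15% of the sample-size section were the conversion rates in agar-positive subjects, f were 20%, and all liquid-only subjects in both arms stayed liquid-only or became negative. The rates become 0.20 + 0.80 × 0.45 = 56% and 0.20 + 0.80 × 0.15 = 32%. The difference falls from 30 to 24 points and the odds ratio from 4.6 to 2.7. But those rates are assumptions about symptom response, not culture, and no odds ratio is planned here. The result also depends on equal behaviour in the two arms: if 80% of liquid-only placebo subjects qualified, the placebo rate would be 0.20 × 0.80 + 0.12 = 28% and the difference 28 points. Subjects who become negative are genuine converters and should not be held against the endpoint.
- **Contradiction with 12.2.10.** That analysis also censors for death, withdrawal and alternative antibiotics, so the two outputs would differ even with the same baseline filter.
- **The subject who is liquid-only at Day 28 and grows on agar at Day 84.** Counting such a subject is largely a feature of any at-any-time endpoint. The Day 84 count in the same bullet scores that subject as not converted.

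**Conclusion.** The definitional error stands. As written, an unchanged liquid-only culture counts as conversion, and liquid-only results fall into both the converter and non-converter groups. This follows from the SAP's own definitions and needs no assumption.

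The size does need one. With a liquid-only share of 0 to 20%, equal in both arms, and no change in those subjects, 0 to 9 of 45 omadacycline and 0 to 6 of 30 placebo subjects would be counted wrongly. At a share near zero the effect vanishes.

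The consequence is confined to one descriptive summary. The documents do not support a claim about the direction or size of bias in a treatment effect. The correction is still worth making, because a stated rule yields a wrong percentage and the SAP already uses the remedy in 12.2.10.

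**What to change.** 1. In SAP 11.1 and 12.3, limit the negative-or-liquid-only conversion endpoint to subjects with MABC growth on agar at baseline (score 2 or higher), as 12.2.10 does.
2. In the 12.3 bullet, define non-conversion as persisting growth on agar, so that the two categories do not overlap.
3. Reconcile the meaning of a positive culture between 12.2.10 (growth in both media) and 12.3 (growth in either).

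Subjects who are liquid-only at baseline then fall outside this endpoint altogether. They remain covered by the separate bullet on conversion to a negative culture and by the planned shift table, so no new output is needed.

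The cost is a few sentences, one programming filter and a slightly smaller denominator. At an assumed liquid-only share of 20%, the denominators would be 45 − 9 = 36 and 30 − 6 = 24.

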13. SAFETY ANALYSES

All safety analyses will be based on the safety analysis set.

13.1 Extent of Exposure

Test article exposure will be summarized for each treatment using the total number of doses taken, total dose received, and the duration of treatment. Subjects are prescribed to take 2 tablets once per day for the duration of the study.

Test article compliance will be calculated as follows:

- Compliance (%): $(\text{actual number of used tablets in total}) / (\text{number of prescribed tablets to be taken per the actual treatment period}) \times 100$
- Actual number of used tablets: number of tablets dispensed – number of tablets returned
- Prescribed number of tablets to be taken: duration of test article administration (days) \times 2 daily tablets
- Duration of test article administration (days) = date of last administration – date of first administration + 1

Test article compliance will be summarized by treatment group using counts and percentages as categorized below:

- >80%
- <=80%

In the event that data regarding the number of tablets "returned" is missing, the compliance calculation will ignore this interval in the calculation of compliance. For example, if a subject completes through Day 56 and is dispensed a final kit, but then is lost to follow up, the expected duration of administration will be calculated through the last dose date recorded on the kit returned at the Day 56 visit and the number of tablets taken will be based on the data from the first 2 kits. Similarly, if data regarding the number of tablets "returned" from the dosing interval between Day 28 and Day 56 is missing then the duration of dosing will be adjusted to remove this interval and the number of tablets taken will be based on recorded data from dosing intervals between Baseline and Day 28, and between Day 56 and Day 84.

13.2 Adverse Events

All AE summaries will be restricted to treatment-emergent AEs (TEAEs), which are defined as those AEs that occurred on or after first dose of test article and those existing AEs that worsened on or after first dose of test article. If it cannot be determined whether the AE is treatment emergent due to a partial onset date, then it will be counted as such. Verbatim terms in the eCRFs will be mapped to SOCs and PTs using MedDRA, version 24.0.

Each AE summary will be displayed by treatment group. Summaries that are displayed by SOC and PTs will be ordered by descending subject count in the total column by SOC and PT. Summaries of the following types will be presented:

- Overall summary of AEs that contains an overview of each of the following points
- Subject incidence of TEAEs and total number of unique TEAEs by MedDRA SOC and PT
- Subject incidence of TEAEs by MedDRA PT shown in order of descending frequency of PT in the omadacycline group
- Subject incidence of TEAEs by MedDRA SOC, PT, and highest severity. At each level of subject summarization, a subject is classified according to the highest severity if the subject reported 1 or more events. Adverse events with missing severity will be considered severe for this summary.
- Subject incidence of TEAEs by MedDRA SOC, PT, and closest relationship to test article (related/not related) as classified by the principal investigator. At each level of subject summarization, a subject is classified according to the closest relationship if the subject reported 1 or more events. Adverse events with a missing relationship will be considered related for this summary.
- Subject incidence of serious TEAEs and total number of unique serious TEAEs by MedDRA SOC and PT
- Subject incidence of TEAEs resulting in death by MedDRA SOC and PT

- Subject incidence of TEAEs leading to test article discontinuation by MedDRA SOC and PT
- Subject incidence of TEAEs leading to study discontinuation by MedDRA SOC and PT
- Subject incidence of TEAEs that occurred with onset date up through Day 15 by MedDRA SOC and PT
- Subject incidence of TEAEs that occurred with onset date after Day 15 by MedDRA SOC and PT

A summary of TEAEs experienced by treatment arm by PT will be provided.

Separate listings of serious AEs (SAEs), AEs resulting in death, AEs leading to test article discontinuation, and AEs leading to study discontinuation will be provided.

